3.3.2 Exclusion Criteria

1. Target Disease Exceptions: EN and EPd Cohorts

- a) Subjects with solitary bone or extramedullary plasmacytoma as the only evidence of plasma cells dyscrasia.
- b) Subjects with monoclonal gammopathy of undetermined significance (MGUS), smoldering multiple myeloma (SMM), primary amyloidosis (no active multiple myeloma), Waldenstrom's macroglobulinemia, or POEMS syndrome (plasma cell dyscrasia with poly neuropathy, organomegaly, endocrinopathy, monoclonal protein, and skin changes)
- c) Subjects with active plasma cell leukemia (defined as either 20% of peripheral blood white blood cell count comprised of plasma/CD138+ cells or an absolute plasma cell count of 2×10^{9} /L)
- d) Subjects with Central Nervous System involvement with multiple myeloma
- 2. Medical History and Concurrent Diseases for both cohorts unless otherwise noted.
 - a) Any serious medical condition, laboratory abnormality, or psychiatric illness that would prevent the patient from signing the informed consent form
 - b) Any serious concurrent medical conditions that may make the patient non-evaluable or put the patient's safety at risk
 - c) Active infection that requires parenteral anti-infective treatment >14 days
 - d) Unable to tolerate thromboembolic prophylaxis while on the study
 - e) Severe hypersensitivity reaction to prior IMiD (thalidomide or lenalidomide)
 - f) Grade > 2 peripheral neuropathy (per National Cancer Institute Common Terminology Criteria for Adverse Events (NCI CTCAE) v3.0)
 - g) Any positive test for hepatitis B virus or hepatitis C virus indicating acute or chronic infection.
 - h) Known HIV infection or known acquired immunodeficiency syndrome (AIDS). NOTE: Testing for HIV must be performed at sites where mandated locally
 - i) Prior or concurrent malignancy, except for the following:
 - i) Adequately treated basal cell or squamous cell skin cancer or in-situ carcinoma.
 - ii) Any other cancer from which the subject has been disease free for > 3 years prior to study entry.

- j) Additionally for EN Cohort:
 - i) Subjects with an active, known or suspected autoimmune disease. Subjects with type I diabetes mellitus, hypothyroidism only requiring hormone replacement, skin disorders (such as vitiligo, psoriasis, or alopecia) not requiring systemic treatment, or conditions not expected to recur in the absence of an external trigger are permitted to enroll
 - Subjects with a condition requiring systemic treatment with either corticosteroids (> 10 mg daily prednisone equivalent) or other immunosuppressive medications within 14 days of initiation of study drug. Inhaled or topical steroids, and adrenal replacement steroid doses > 10 mg daily prednisone equivalent, are permitted in the absence of active autoimmune disease

3. Prior therapy or surgery

a) For EPd Cohort

- i) Prior treatment with pomalidomide
- ii) Prior participation in an elotuzumab clinical trial regardless of treatment assignment.
- iii) Prior discontinuation of treatment with elotuzumab due to intolerable drug-related adverse reactions
- iv) Use of any anti-myeloma drug therapy within 14 days of the initiation of study drug treatment or use of any experimental drug therapy within 28 days of the initiation of study drug treatment
- v) Treatment with melphalan within 4 weeks of the first dose of study drug
- vi) Treatment with corticosteroids (other than the dexamethasone of anti-myeloma regimens) within 3 weeks of the first dose of study drug, except for the equivalent of ≤ 10 mg prednisone per day or corticosteroids with minimal to no systemic absorption (ie, topical or inhaled steroids)
- vii) Prior autologous stem cell transplant within 12 weeks of the first dose of study drug
- viii) Prior allogeneic stem cell transplant except subjects who have completed the stem cell transplant > 12 months prior to first dose of study drug, have no history of graft versus host disease, and are not on systemic immunosuppressive therapy
- ix) Major cardiac surgery within 8 weeks prior to the first dose of study drug; all other major surgery within 4 weeks prior to the first dose of study drug.

b) For EN Cohort

- i) Prior treatment with elotuzumab or nivolumab (or any PD-1 or PD-L1 inhibitor).
- ii) Use of any anti-myeloma drug therapy, within 14 days of the initiation of study drug treatment. Bisphosphonate use permitted if initiated prior to first dose of study medication
- iii) All prior drug-related AEs should have resolved or returned to baseline for the subject to be eligible
- iv) Prior autologous stem cell transplant within 12 weeks of the first dose of study drug
- v) Prior allogeneic stem cell transplant or graft versus host disease (GVHD) within 12 months of the first dose of study drug, or subjects on topical or systemic immunosuppressive therapy for GVHD
- vi) Treatment with corticosteroids within 2 weeks of the first dose of study drug, except for the equivalent of ≤ 10 mg prednisone per day or corticosteroids with minimal to no systemic absorption (ie, topical or inhaled steroids) or for short course (≤ 4 days) of

40 mg dexamethasone or equivalent for emergency use (baseline M proteins must be drawn after this short course and prior to randomization). Adrenal replacement steroid doses > 10 mg daily prednisone equivalent, are permitted in the absence of active autoimmune disease

vii) Major cardiac surgery within 8 weeks prior to the first dose of study drug; all other major surgery within 4 weeks prior to the first dose of study drug. (Kyphoplasty is not considered major surgery); subjects should have been fully recovered from any surgical related toxicities

4. Physical and Laboratory Test Findings - For both cohorts:

- Absolute neutrophil count $< 1 \times 10^9$ /L (without growth factor support within 1 week)
- Platelets $< 75 \times 10^9/L$ ($< 30 \times 10^9/L$ if $\ge 50\%$ of bone marrow nucleated cells were plasma cells) (without transfusion support within 3 days)
- Creatinine clearance < 30 ml/min according to the Cockroft-Gault formula:
 - Female $CrCl = (140 age in years) \times weight in kg \times 0.85$ 72 x serum creatinine in mg/dl
 - Male CrCl = (140 age in years) x weight in kg x 1.00
 - 72 x serum creatinine in mg/dl
- Total bilirubin $\ge 2 \times ULN (\ge 3 \times ULN \text{ if Gilbert's syndrome})$
- AST or ALT \ge 3x ULN

5. Allergies and Adverse Drug Reaction (For both Cohorts)

a) Known severe hypersensitivity or allergy to dexamethasone, any excipients in elotuzumab, formulation or recombinant protein, or any monoclonal antibody

6. Other Exclusion Criteria (For both Cohorts)

- a) Prisoners or subjects who are involuntarily incarcerated
- b) Subjects who are compulsorily detained for treatment of either a psychiatric or physical (eg, infectious disease) illness

3.3.3 Women of Childbearing Potential

A Women of childbearing potential (WOCBP) is defined as any female who has experienced menarche and who has not undergone surgical sterilization (hysterectomy or bilateral oophorectomy) and is not postmenopausal. Menopause is defined as 12 months of amenorrhea in a woman over age 45 years in the absence of other biological or physiological causes. In addition, females under the age of 55 years must have a serum follicle stimulating hormone, (FSH) level > 40mIU/mL to confirm menopause.

*Females treated with hormone replacement therapy, (HRT) are likely to have artificially suppressed FSH levels and may require a washout period in order to obtain a physiologic FSH level. The duration of the washout period is a function of the type of HRT used. The duration of the washout period below are suggested guidelines and the investigators should use their judgment in checking serum FSH levels. If the serum FSH level is > 40 mIU/ml at any time during the washout period, the woman can be considered postmenopausal:

• 1 week minimum for vaginal hormonal products (rings, creams, gels)

- 4 week minimum for transdermal products
- 8 week minimum for oral products

Other parenteral products may require washout periods as long as 6 months.

3.3.4 Eligibility Criteria for EN Patients to Cross-over to EPd cohort.

Crossover to EPd is permitted if:

- No clinical benefit (\geq minimal response) after 2 cycles.
- No objective response (\geq PR) after 5 cycles of treatment.

EN patients who cross-over will no longer be treated with nivolumab after the cross-over to the EPd cohort. Re-consent is not required for EN patients who cross-over to treatment with EPd.

EN patients who do not cross-over can continue treatment with EN until discontinuation criteria are met, as specified in Section 3.5.

Eligibility criteria for this study have been carefully considered to ensure the safety of the study subjects and that the results of the study can be used. It is imperative that subjects fully meet all eligibility criteria.

	_	

Revised Protocol No.: 03 Date: 08-Mar-2018

Revised Protocol No.: 03 Date: 08-Mar-2018

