3. INVESTIGATIONAL PLAN

3.1 Study Design and Duration

This is a Phase 2, multi-center, open-label, multiple cohort study of elotuzumab in combination with pomalidomide and low-dose dexamethasone (EPd Cohort) and elotuzumab in combination with nivolumab (EN Cohort) to assess the safety and efficacy of these combination therapies for treatment of relapsed or refractory MM patients.

In the EPd Cohort, subjects will receive treatment with elotuzumab in combination with pomalidomide and low-dose dexamethasone in a 28 day cycle. Subjects will receive 10 mg/kg IV elotuzumab on Days 1, 8, 15, and 22 of Cycles 1 and 2. Starting with Cycle 3, subjects will receive 20 mg/kg on Day 1.

As of Amendment 02, subjects will also be enrolled in the EN cohort to receive a combination of elotuzumab and nivolumab in a 28-day cycle. EN subjects will receive nivolumab 240 mg IV on Days 1 and 15 for Cycles 1-4. At Cycle 5 and beyond, subjects will receive 480 mg IV on Day 1. Subjects will also receive elotuzumab 10 mg/kg on Days 1, 8, 15, and 22 of Cycles 1 and 2. At Cycle 3 and beyond, subjects will receive 20 mg/kg of elotuzumab IV on Day 1. If subjects do not achieve clinical benefit represented by at least minimal response (\geq MR) after 2 cycles of treatment or do not achieve an objective response (\geq PR) after 5 cycles of treatment, they may cross over to the EPd cohort at Day 1 of the subsequent cycles if they also meet the eligibility criteria for cross-over specified in Section 3.3.4.

Subjects will continue treatment as long as the subject has clinical benefit from the treatment and do not meet criteria for discontinuation.

All subjects will be assessed for safety and response as presented in the Time and Event Tables in Section 5. Subjects who are discontinued from further study treatment for reasons other than progression will be followed for disease progression. Following disease progression, subjects will be followed at least annually for survival.

Approximately 120 subjects will be screened in this study. A minimum of 60 subjects will be treated in the EPd Cohort. Approximately 30 subjects will be treated in the EN Cohort. The estimated duration of enrollment is 18 to 24 months, and the duration of the study is estimated at 48 months from the date of first patient, first visit. Per Revised Protocol 03, the EPd cohort is closed for enrollment.

The study design schematic is presented in Figure 3.1-1.

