3.5 Discontinuation of Subjects following any Treatment with Study Drug

Subjects MUST discontinue investigational product (and non-investigational product at the discretion of the investigator) for any of the following reasons:

- Subject's request to stop study treatment
- Any clinical adverse event (AE), laboratory abnormality or intercurrent illness which, in the opinion of the investigator, indicates that continued participation in the study is not in the best interest of the subject
- Termination of the study by Bristol-Myers Squibb (BMS) or meeting the criteria for stopping rules for cohort(Section 4.5.10).
- Loss of ability to freely provide consent through imprisonment or involuntary incarceration for treatment of either a psychiatric or physical (eg, infectious disease) illness
- Pregnancy (Subjects must discontinue the study drugs.
- Progressive Disease (Appendix 4)
- Subjects who receive any non-protocol specified systemic anti-myeloma therapy before documented progression will be discontinued from all study treatment (including pomalidomide/dexamethasone); however, tumor assessments will continue at 4 week intervals until documented progression.
- Subjects experiencing a Grade 4 infusion reaction related to elotuzumab must discontinue elotuzumab (refer to the Grade 4 Infusion Reaction subsection presented in Section 4.5.5) Subjects may continue pomalidomide and dexamethasone treatment.
- Subjects experiencing a Grade 3 or 4 infusion reaction related to nivolumab must discontinue nivolumab (only).
- Subjects experiencing angioedema, Grade 4 rash, exfoliative or bullous rash, Stevens-Johnson syndrome, or toxic epidermal necrolysis related to pomalidomide must discontinue pomalidomide. Subjects may continue elotuzumab and dexamethasone.
- Subjects experiencing a 56 day delay in all study drugs (elotuzumab, nivolumab, pomalidomide, and dexamethasone) due to an adverse event(s) related to study treatment must be discontinued from study drug. Subjects experiencing delays unrelated to study therapy, for example due to radiation therapy may delay study treatment up to 84 days. Further delays may be allowed after discussion with the medical monitor.

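### The EN-to-EPd crossover rule rests on non-response alone and so takes in subjects with progressive disease, for whom Section 3.5 requires investigational product to stop; the passages must be reconciled

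*Protocol*

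**What the plan says.** Section 3.1 of the protocol lets EN subjects cross over after 2 or 5 cycles "if they also meet the eligibility criteria for cross-over specified in Section 3.3.4". Section 3.3.4 introduces its list with "Crossover to EPd is permitted if" and gives two entries: no "minimal response) after 2 cycles", and no "PR) after 5 cycles of treatment". It states no conjunction between them; Section 3.1 and the Synopsis join them with an or. SAP Section 2.1 repeats the rule, with a broken reference where the protocol section number should be.

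Section 3.5 begins "Subjects MUST discontinue investigational product (and non-investigational product at the discretion of the investigator) for any of the following reasons", and one bullet reads "Progressive Disease (Appendix 4". The bullet is not limited by cohort or by drug. Table 4.-1 lists elotuzumab, nivolumab and pomalidomide as investigational and dexamethasone as non-investigational. Section 3.3.4 mentions Section 3.5 once, for EN patients who do not cross over.

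The EPd exclusions in Section 3.3.2 (item 3.a) begin with "Prior treatment with pomalidomide". The EN exclusions (item 3.b) do not name pomalidomide, and the EN inclusion criterion asks for a prior immunomodulatory agent without saying which.

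**The concern.** A site with an EN subject who has progressed by the end of Cycle 2 will look in Section 3.3.4 and find that crossover is allowed, then look in Section 3.5 and find that two of the three EPd drugs must stop. Nothing ranks one passage above the other, so sites may act differently on the same facts. That affects who receives EPd after EN. It could also affect overall survival in the EN cohort, a secondary endpoint that runs from first dose to death with no censoring at crossover.

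The second issue is that Section 3.1 promises further crossover criteria, but Section 3.3.4 only restates non-response. A site cannot tell whether any EPd exclusion still applies to a subject crossing over.

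**Working it through.** The plan states no figure on this point, so the check sets the texts side by side.

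1. **Does the crossover rule include progressors?** The response categories in Appendix 4 make PD separate from, and worse than, MR and PR. A subject with PD has no MR or better after 2 cycles, and a subject who progresses later without a PR has no PR or better after 5. Neither condition in Section 3.3.4 excludes PD.

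2. **Can PD be established by the time of crossover?** Cycles are 28 days and anchored to Cycle 1 Day 1, response is assessed every 4 weeks, and the EN schedules (Tables 5.1-4 to 5.1-6) require two consecutive assessments for PD. Cycle 2 Day 1 is study day 28 + 1 = 29. Cycle 3 Day 1 is 2 × 28 + 1 = 57. PD first seen on day 29 can be confirmed on day 57, which is the first crossover visit. The later one, Cycle 6 Day 1, is day 5 × 28 + 1 = 141.

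3. **What would stop?** EPd is elotuzumab, pomalidomide and dexamethasone. Under Table 4.-1 the first two are investigational, so the PD bullet of Section 3.5 reaches both.

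4. **Do the EPd entry criteria apply at crossover?** EPd requires 1 to 2 prior lines and EN requires at least 4. Since 4 > 2, no subject can satisfy both. Exclusion 3.a.ii (prior participation in an elotuzumab trial), read literally, would also reach EN subjects. Exclusion 3.a.iv (14 days free of anti-myeloma drugs) would fail at the first crossover visit on full dosing: the last elotuzumab dose, Cycle 2 Day 22, is study day 28 + 22 = 50, and 57 − 50 = 7 days. Crossover is therefore workable only if Section 3.3.4 replaces at least part of the EPd criteria. No section in the public text says which part.

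5. **Result by type of EN subject at a crossover time point**

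| Subject | Section 3.3.4 | Other rule | Result |
|---|---|---|---|
| Confirmed PD | permits EPd | Section 3.5 stops investigational product | conflict |
| Stable disease, no prior pomalidomide | permits EPd | PD bullet not triggered | no conflict |
| Stable disease, prior pomalidomide | permits EPd | 3.a.i bars EPd only if it carries over | not addressed |

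6. **Follow-up after crossover.** Table 5.1-3 covers crossover subjects and schedules response assessment every 4 weeks until progression. It does not say whether, for them, that means progression on EN or on EPd.

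**The case against.** The strongest reply is that a permission and a prohibition can be read together. Section 3.3.4 says crossover is allowed and Section 3.5 says stopping is mandatory, so the mandatory rule prevails and progressors are out. Section 3.1 supports this: straight after the crossover text it says treatment continues only while discontinuation criteria are unmet. SAP Section 2.1 also shows that progression is named when it is meant as a trigger, in its text on adding nivolumab in the EPd cohort. This is a fair reading, but it is not the only one. Because Section 3.3.4 cites Section 3.5 only for patients who stay on EN, a site could equally conclude that PD ends EN and opens EPd. Other bullets of Section 3.5 say so when a stop is confined to one drug; the PD bullet does not. The two readings lead to opposite actions, so the text needs a decision.

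Some stronger readings do not hold:

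- **Prior pomalidomide as a second contradiction.** A reader might infer that a pomalidomide-exposed EN subject is both admitted and barred. Exclusion 3.a.i governs entry to a cohort now closed to enrolment, and Section 3.3.4 is headed as a separate set of criteria. Applying the EPd criteria in full would bar every EN subject, so silence on this item is a gap.
- **A history of severe pomalidomide reaction goes unchecked.** Exclusion 2.e names only two drugs: "Severe hypersensitivity reaction to prior IMiD (thalidomide or lenalidomide". However, medical and treatment history is taken at screening, exclusion 2.b covers serious conditions that put safety at risk, and EN exclusion 3.b.iii concerns earlier drug-related events. What is true is only that no explicit criterion names pomalidomide.
- **Progressors who cross over have no scheduled response data.** That assumes progression in Table 5.1-3 means progression on EN, which the table does not say.

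**Conclusion.** The conflict is real but narrow. It concerns EN subjects whose disease has progressed at a crossover time point: Section 3.3.4 permits EPd and Section 3.5 requires two of its drugs to stop. Apart from that, the protocol leaves open which EPd exclusions carry over.

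The number of subjects affected cannot be derived. A reader might take the 30% response rate of Section 8.1.2, giving 0.30 × 30 = 9 responders and 30 − 9 = 21 non-responders, and call all 21 affected. The documents do not support that. The 30% illustrates the width of a confidence interval and is not a planning assumption, and the 21 would include subjects with stable disease or MR, who are not in conflict. The documents give neither an early-progression rate nor the share of EN subjects with prior pomalidomide.

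The conclusion rests on the public text, which does not contain Section 3.4. Section 4.2 cites 3.4.1 for thromboprophylaxis; a further restriction on crossover there cannot be ruled out, although the list in Section 3.3.4 itself appears complete.

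**What to change.** - Reconcile Section 3.3.4, Section 3.1, the Synopsis and SAP Section 2.1 with the PD bullet of Section 3.5. State whether a subject with confirmed PD on EN may cross over, and add the matching exception or cross-reference in Section 3.5. Repair the broken reference in SAP Section 2.1 at the same time.
- In Section 3.3.4, state which exclusions under item 3.a of Section 3.3.2, if any, apply at crossover, with prior pomalidomide addressed explicitly.
- In Table 5.1-3, say whether assessment of crossover subjects ends at progression on EN or on EPd.
- In the SAP, add a listing of crossover subjects by PD status at crossover and by prior pomalidomide. The 4-weekly response assessments and the eCRF page on prior systemic therapy (SAP Section 7.3.4) already supply the data.

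Which clinical rule applies is for the sponsor to decide. The cost is an amendment of wording, one table note and one listing. Depending on the decision, either some subjects lose the crossover option or Section 3.5 gains an exception.

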3.5 Discontinuation of Subjects following any Treatment with Study Drug

Subjects MUST discontinue investigational product (and non-investigational product at the discretion of the investigator) for any of the following reasons:

- Subject's request to stop study treatment
- Any clinical adverse event (AE), laboratory abnormality or intercurrent illness which, in the opinion of the investigator, indicates that continued participation in the study is not in the best interest of the subject
- Termination of the study by Bristol-Myers Squibb (BMS) or meeting the criteria for stopping rules for cohort(Section 4.5.10).
- Loss of ability to freely provide consent through imprisonment or involuntary incarceration for treatment of either a psychiatric or physical (eg, infectious disease) illness
- Pregnancy (Subjects must discontinue the study drugs.
- Progressive Disease (Appendix 4)
- Subjects who receive any non-protocol specified systemic anti-myeloma therapy before documented progression will be discontinued from all study treatment (including pomalidomide/dexamethasone); however, tumor assessments will continue at 4 week intervals until documented progression.
- Subjects experiencing a Grade 4 infusion reaction related to elotuzumab must discontinue elotuzumab (refer to the Grade 4 Infusion Reaction subsection presented in Section 4.5.5) Subjects may continue pomalidomide and dexamethasone treatment.
- Subjects experiencing a Grade 3 or 4 infusion reaction related to nivolumab must discontinue nivolumab (only).
- Subjects experiencing angioedema, Grade 4 rash, exfoliative or bullous rash, Stevens-Johnson syndrome, or toxic epidermal necrolysis related to pomalidomide must discontinue pomalidomide. Subjects may continue elotuzumab and dexamethasone.
- Subjects experiencing a 56 day delay in all study drugs (elotuzumab, nivolumab, pomalidomide, and dexamethasone) due to an adverse event(s) related to study treatment must be discontinued from study drug. Subjects experiencing delays unrelated to study therapy, for example due to radiation therapy may delay study treatment up to 84 days. Further delays may be allowed after discussion with the medical monitor.

In the case of pregnancy, the investigator must immediately notify the BMS Medical Monitor/designee of this event, and treatment with the IMPs would immediately be stopped. In most cases, the study drug will be permanently discontinued in an appropriate manner. Please call the BMS Medical Monitor within 24 hours of awareness of the pregnancy. If the investigator

determines a possible favorable benefit/risk ratio that warrants continuation of study drug (ie, allowing restart of study drug if the patient choses to terminate the pregnancy), a discussion between the investigator and the BMS Medical Monitor/designee must occur so that permission can be granted.

All subjects who discontinue study drug should comply with protocol-specified follow-up procedures outlined in Section 5. The only exception to this requirement is when a subject withdraws consent for all study procedures including post-treatment study follow-up or loses the ability to consent freely (ie, is imprisoned or involuntarily incarcerated for the treatment of either a psychiatric or physical illness).

If study drug is discontinued prior to the subject's completion of the study, the reason for the discontinuation must be documented in the subject's medical records and entered on the appropriate case report form (CRF/eCRF) page.

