4.5.8 Dose Delay, Interruption, or Discontinuation for All Subjects

Please refer to Sections 4.5.8.1, 4.5.8.2, 4.5.8.3, and 4.5.8.4 for drug-specific delay guidance.

For each cohort, if the dose of one drug in the regimen (ie, pomalidomide, dexamethasone, nivolumab, or elotuzumab) is delayed, interrupted, or discontinued, the treatment with the other drugs may continue as scheduled. However, in the EPd cohort, if dexamethasone is delayed or discontinued discuss ongoing elotuzumab administration with the Medical Monitor. Subjects experiencing a 56 day delay in all study drugs due to an adverse event(s) related to study treatment must be discontinued from study drug. Subjects experiencing delays unrelated to study therapy, for example due to radiation therapy, may delay study treatment after discussion with the medical monitor.

Each cycle is 28 days. While dose delays or interruptions are permitted, the start of each cycle cannot be delayed and is fixed (ie, anchored) relative to Cycle 1 Day 1. Adjustments to the Cycle 1 Day 1 anchored schedule should not be performed. Missed doses should be skipped, not delayed, if not given within the allowed window.

Subjects may continue on study therapy even if components of the study therapy must be discontinued. For example, a subject may continue on study therapy if elotuzumab must be discontinued for an adverse event or other reason. Patients are considered still on study therapy even if they continue solely on pomalidomide, dexamethasone, or nivolumab.

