- Any event that leads to delay in dosing lasting > 8 weeks from the previous dose requires discontinuation, with the following exceptions:
 - Dosing delays to allow for prolonged steroid tapers to manage drug-related adverse events are allowed. Prior to re-initiating treatment in a subject with a dosing delay lasting > 8 weeks from the previous dose, the BMS medical monitor must be consulted. Tumor assessments should continue as per protocol even if dosing is delayed/interrupted. Periodic study visits to assess safety and laboratory studies should also continue as clinically indicated during such dosing delays/interruption.
 - Dosing delays lasting > 8 weeks from the previous dose that occur for non-drug-related reasons may be allowed if approved by the BMS medical monitor. Prior to re-initiating treatment in a subject with a dosing delay lasting > 8 weeks, the BMS medical monitor must be consulted. Tumor assessments should continue as per protocol even if dosing is delayed/interrupted. Periodic study visits to assess safety and laboratory studies should also continue as clinically indicated during such dosing delays/interruption.
- Any adverse event, laboratory abnormality, or intercurrent illness which, in the judgment of the Investigator, presents a substantial clinical risk to the subject with continued nivolumab dosing.

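### Protocol Sections 3.5, 4.5.8 and 4.5.8.6 are not aligned on how long treatment may be delayed, when the medical monitor is involved, and whether an EN subject with all drugs held for a steroid taper may restart

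*Protocol*

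**What the plan says.** **Unrelated delays.** Protocol Section 3.5 says that subjects whose delay is unrelated to study therapy, with radiation as the example, "may delay study treatment up to 84 days". It then adds: "Further delays may be allowed after discussion with the medical monitor". Section 4.5.8 takes the same situation and the same example, but says that these subjects "may delay study treatment after discussion with the medical monitor", with no number of days. Section 4.5.8.6, which concerns nivolumab, says that delays of more than 8 weeks from the previous dose "that occur for non-drug-related reasons may be allowed if approved by the BMS medical monitor".

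**Related adverse events.** Section 3.5 addresses "Subjects experiencing a 56 day delay in all study drugs" and says that such a delay "due to an adverse event(s) related to study treatment must be discontinued from study drug". Section 4.5.8 repeats the rule. Neither sentence contains an exception. Section 4.5.8.6 sets a nivolumab limit of more than 8 weeks from the previous dose and then lists exceptions, the first being: "Dosing delays to allow for prolonged steroid tapers to manage drug-related adverse events are allowed". Before nivolumab is restarted after more than 8 weeks, the medical monitor must be consulted.

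**Links between the sections.** Section 3.3.4 sends EN subjects who do not cross over to Section 3.5 for their discontinuation criteria. Section 4.5.8.5 refers to the exceptions in 4.5.8.6. Section 4.5.8 refers to 4.5.8.1 to 4.5.8.4 for drug-specific delay guidance, but not to 4.5.8.6. The delay sentences in 3.5 refer to none of these. Nothing states which section prevails.

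**The concern.** A site handling a long interruption has to answer three questions: whether the subject must stop, whether the medical monitor has to be involved, and from which date the days are counted. The answers depend on which section the site opens. After an immune-related event in the EN cohort, whether the subject stops or restarts is a safety decision.

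The answer also reaches the reported data. SAP Section 7.4.4 tabulates reasons for stopping study treatment. SAP Section 7.4.1.10 computes nivolumab dose intensity over a period whose end depends on the last cycle dosed and on the discontinuation date. Two subjects with the same history could therefore be managed and recorded differently.

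**Working it through.** The plan gives no figure to reproduce. The check sets the rules side by side, followed by simple day counts.

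**Step 1. The rules by situation**

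| Situation | Section 3.5 | Section 4.5.8 | Section 4.5.8.6 (nivolumab, so EN only) |
|---|---|---|---|
| Unrelated delay | Up to 84 days; discussion attached to longer delays | No day limit; discussion is a condition | Approval once beyond 8 weeks from the previous dose |
| Related event, only one EN drug held | 56-day rule not triggered | Not triggered; the other drugs may go on | 8-week limit with its exceptions |
| Related event, all drugs held, prolonged steroid taper | Stop at 56 days | Stop at 56 days | Delay allowed; nivolumab may restart after consultation |

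The first row is a misalignment between 3.5 and 4.5.8 in both cohorts, with a third requirement for nivolumab. The second row shows no conflict. The third row gives opposite outcomes.

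**Step 2. Can the third row occur?** Yes. Under Table 4.5.2-2, footnote b, an EN subject receives no dexamethasone when elotuzumab is skipped. Holding elotuzumab and nivolumab therefore holds every drug in the EN regimen.

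**Step 3. An unrelated delay, worked through.** Take an EN subject 60 days after the previous nivolumab dose, with 8 weeks = 8 × 7 = 56 days.
- Section 3.5: 60 < 84, so the delay is allowed and no monitor step is stated.
- Section 4.5.8: discussion is required.
- Section 4.5.8.6: 60 > 56, so approval is required.

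**Step 4. The clocks.** Section 4.5.8.6 counts from the previous dose. Sections 3.5 and 4.5.8 count a delay without saying when it begins, and 4.5.8 also says that doses missed outside their window are skipped rather than delayed. Assume, for illustration only, that a delay begins on the missed scheduled date. The planned nivolumab interval is 14 days in Cycles 1 to 4 and 28 days from Cycle 5.
- A 56-day delay is then 56 + 14 = 70 or 56 + 28 = 84 days from the previous dose.
- An 84-day delay is 84 + 14 = 98 or 84 + 28 = 112 days from the previous dose.
- The nivolumab limit is passed once a dose is more than 56 − 14 = 42 or 56 − 28 = 28 days late.

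**Step 5. What the choice does to reported exposure.** Take a hypothetical EN subject with 480 mg on Day 1 of Cycles 5 and 6, counting Cycle 5 Day 1 as day 0. Both antibodies are then held for a taper. The Cycle 7 dose, due on day 56, is missed. Cycle 9 Day 1 is day 112, which is 112 − 28 = 84 days from the previous dose and 112 − 56 = 56 days after the missed date. Using the SAP formula for Cycle 5 and beyond, with planned intensity 120 mg/week:
- Stopped: the period ends at 28 + 28 = day 56, before any discontinuation under the 56-day rule. Intensity is 7 × 960 / 56 = 120 mg/week, or 100% relative.
- Restarted with one dose in Cycle 9: the period ends at 112 + 28 = day 140. Intensity is 7 × 1,440 / 140 = 72 mg/week, or 60% relative.

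The same interruption is left out of the denominator in one case and counted in the other. This is one constructed subject, not an estimate for the cohort.

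**The case against.** The best defence is that the sections can be obeyed together. The 56-day rule acts on the subject and only when all drugs are held, whereas 4.5.8.6 acts on nivolumab, and its taper sentence is an exception to its own limit. Escaping one stopping criterion need not cancel another. On unrelated delays a site could always discuss, obtain approval for nivolumab beyond 8 weeks, and treat 84 days as a further checkpoint. Restart of nivolumab after more than 8 weeks also passes through the sponsor's medical monitor, which gives some central consistency.

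Part of this stands. The stop-versus-restart conflict disappears if any drug continues or if no prolonged taper is involved. The absence of a monitor step before 84 days is inferred from where 3.5 places its discussion sentence; it is not stated. But the reading that makes everything compatible is not written anywhere. Section 4.5.8.5 shows that the authors cross-refer to 4.5.8.6 when an exception is meant, and the 56-day sentences do not. If the discussion sentence in 3.5 were taken to soften the related-event rule as well, 4.5.8 would still repeat that rule without it.

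Several stronger readings are tempting and are not supported:
- That delays of 57 to 84 days form a 28-day band free of approval in one section and not in another. Subtracting 56 from 84 assumes a common clock.
- That every delay from day 1 to day 84 is treated differently by 3.5 and 4.5.8. Sections 4.5.4 and 4.5.8.1 already permit short delays within dosing windows with no monitor step.
- That the inconsistency weakens the EN toxicity stopping rule or matters more because there is no data monitoring committee. Section 4.5.10 is triggered by Grade 5 and immune-related events, not by delays or discontinuations.
- That ORR or PFS is affected. Sections 3.6 and 5.4.1 continue PFS follow-up and tumour assessment after study drug stops, and no route to ORR is shown.

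**Conclusion.** The three sections are inconsistent and should be reconciled. For unrelated delays the misalignment between 3.5 and 4.5.8 applies to both cohorts, and 4.5.8.6 adds a separate approval step for nivolumab. For related events the contradiction is confined to EN subjects with all study drugs held for a prolonged steroid taper. The documents give no basis for estimating how many subjects that is.

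The conclusion assumes that holding all study drugs means all drugs in the subject's own regimen, and that no unstated convention ranks the sections. The consequences lie in stopping and restart decisions, exposure summaries, and the date and reason of discontinuation. The point is one of internal consistency with a safety aspect; it does not threaten the primary analyses.

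**What to change.** Reconcile Sections 3.5, 4.5.8 and 4.5.8.6 into one rule per situation: related or unrelated cause; one drug or all drugs held; prolonged steroid taper or not. For each, state the limit, if any, and whether the medical monitor is to be informed, consulted or asked to approve. Define the date from which a delay is counted and use it throughout. Say explicitly how the all-drug 56-day rule relates to the exceptions in 4.5.8.6, and cross-refer from 3.5 and 4.5.8 to the reconciled text.

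Which limit and which monitor step applies is for the sponsor's clinical team to decide. The cost is a protocol clarification. Sample size, endpoints and planned analyses do not change.
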